10.5 Other reportable events

Reporting timeframes begin when the site learns of the occurrence of the event.

Event	Definition	Reporting
Breach of confidentiality	The exposure of any study information or communications directly related to a study subject to anyone not named as study staff or the release of a study subject's identifiable information to study staff who were not specified to receive such information in the protocol or IRB application.	Treat as major deviation (below)
Protocol deviation	A deviation is an incident involving a departure from the IRB-approved protocol in the actual conduct of the study. Deviations may result from the action of the participant, investigator, or staff.	See below
Major deviations	Deviations are considered major when the unapproved change(s) in previously approved research activities, implemented without IRB approval, may potentially adversely affect subjects' rights, safety, welfare, or willingness to continue participation, or affect the scientific	Treat as an Unanticipated Problem (above)

	design of the study and/or the integrity of the resultant data.	
Minor deviations	Deviations are considered minor when the unapproved change(s) in previously approved research activities, implemented without IRB approval, do not adversely affect subjects or the integrity of the study data.	Sites are to report cumulative events to AE Coordinator at time of continuing review.
Protocol violation	An incident involving an intentional deviation from the IRB-approved protocol that was not implemented in response to an emergency situation and that may impact a subject's rights, safety, and/or welfare, makes a substantial alteration to risks to subjects, or affects the scientific design of the study and/or the integrity of the resultant data. Violations may also be repeated deviations (major or minor) of the same nature. Violations can represent serious or continuing non-compliance with the federal regulations and guidelines for ethical conduct of human subject research.	Treat as an Unanticipated Problem (above)
Protocol Exceptions	A protocol exception is an IRB-approved deviation for a single subject or a small group of subjects, but is not a permanent revision to the research protocol.	Protocol exceptions must be approved by the IRB prior to implementation.

11. Trial safety monitoring

11.1 Data Safety Monitoring Committee

Study team investigators and coordinators will monitor adverse events (AEs) and unanticipated problems (UPs) involving risks to subjects or others and will report them to the Principal Investigator.

- Study team investigators and coordinators will record AEs or UPs and communicate them amongst research team members.
- A Data and Safety Monitoring Board (DSMB) does not exist for this study, however we will convene a committee if needed (see 11.2)
- AEs and UPs will be monitored weekly by the PI and any events related to the study that meet posted required reporting guidance will be reported to the IRB.
- If a subject withdraws prematurely, the data collected will not be included in the final study. [11.2](#)

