6.2 Recruitment and consent

For those patients meeting criteria, they will be approached by the anesthesiologist designated to care for them on the day of surgery. That anesthesiologist will then recruit the patient for the study in the pre-operative holding area. In order to ensure the candidate's privacy and confidentiality, the discussion will take place in pre-operative holding area with the cubicle's curtain and room door closed. In a tone of voice insufficient for others to overhear the conversation and in the presence of only those immediately accompanying the patient and those who are directly involved with the patient's care, the

candidate's eligibility will again be verified against the study enrollment criteria. For candidates with confirmed study enrollment eligibility, the study purpose, procedures, risks, benefits, and alternatives will then be discussed by a study staff member. The written information about the study provided to the candidate at the time of their check-in will be reviewed and they will be instructed to take up to 90 minutes to consider participation. A study member will conduct the informed consent discussion and obtain informed consent and a study physician will be available at all times for any consent-related questions. Any questions that the candidate may have will be answered. Undue coercion will be prevented by stressing that the potential subject does not have to agree to participation and that the future care of the potential subject will not change regardless of the decision about participation. If the candidate has no further questions and would like to participate, they will be asked to sign the written informed consent document.

7. Activities and measurements

Prior to the procedure:

The subject will be met in the preoperative area by a staff anesthesiologist, who interviews and examines the subject. A full explanation of general anesthesia and quadratus lumborum block, including risks, benefits, and alternatives, will be given and informed consent for anesthetic services obtained.

Subjects will be asked to rate their pain at rest using a Numerical Rating Scale (NRS) (0-10) where 0 represents no pain and 10 represents the worst pain imaginable.

Study Randomization:

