The patient will be contacted via phone at 24 hours, 48 hours, and 7 days to assess satisfaction with regional anesthesia, pain at rest, pain with activity, opioid consumption, nausea, pain disturbing sleep, and location of most severe pain. Duration of hospitalization will be obtained from review of medical record. Subjects with new or persistent complaints at 7 days post-surgery that could be related to the study procedures will be offered continued follow-up by telephone. Follow-up procedures would depend greatly on the clinical presentation but could include imaging, specialist consultation or surgical intervention. Subjects without complaints will be given appropriate information for contacting the research team if such complaints arise.

Concomitant Medications:

Analgesic and anti-emetic requirements for block placement, intraoperatively, and in PACU will be extracted from the patient's electronic medical record.

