7.2 Subject withdrawals

At any point prior to or during the intervention period, the subject's clinical care team or a study physician may decide the subject should be withdrawn from the study. Additionally, a subject may at any point elect to withdraw themselves from the study. If a subject is withdrawn from the study for any reason the subject will then be followed according to standard of care follow-up.

Study intervention will immediately stop and subject's clinical care team and a study physician will be immediately notified if the subject suffers a severe adverse perioperative outcome.

In the event the study method is terminated, the reason for termination will be documented on a case report form.

8. Data analysis and statistical considerations

All data will be summarized using standard descriptive statistics, including mean, standard deviation, minimum, maximum, median, inter-quartile range, and confidence intervals, as appropriate. The data will be presented graphically (where possible) using scatter plots, profile plots, or histograms. Data analyses will be performed on an intent-to-treat basis based upon assignment to a treatment arm using SAS (SAS Institute Inc., Cary, NC; version 8.2 or greater) or other statistical software. The primary analysis will consist of comparing the two groups for superiority. For all tests, statistical significance will be defined as a p-value less than 0.05. Repeated measures ANOVA will be used to analyze comparisons made across multiple time points. Patients with missing longitudinal data will be handled by either using data imputation methods to replace the missing data or via alternative analyses tolerant of missing data values. Holm-Bonferroni correction will be used to control familywise error rates for comparisons across multiple time points.

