8.1 Sample size determination

The primary outcome for this study will compare resting NRS pain scores on POD1 between the QLB and medical management groups. A previous study of laparoscopic ventral hernia surgery reported an average POD1 pain score of 4.5 +/- 2.2 NRS (Fields et al, 2015). This average pain score is in keeping with our experience with patients after having laparoscopic ventral hernia surgery at UW-Madison. We feel that a reduction in pain of 2 NRS on POD1 would be meaningful for patients and their physician teams. Therefore, we will power this study to an effect size of 2 NRS. We will accept a type 1 error rate of 0.05 and 80% power. Using these metrics, the study will require a sample size of 21 patients in each group to

detect a statistical difference. To account for patients dropping out or not completing the study, we will enroll 24 patients in each group for a total of 48 patients.

9. Risks and benefits of trial participation

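### Section 11.1 drops the data of subjects who withdraw, while section 8 promises intent-to-treat analysis by assigned arm

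*Combined protocol and SAP*

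**What the plan says.** Section 8 sets the analysis population: "Data analyses will be performed on an intent-to-treat basis based upon assignment to a treatment arm". On incomplete data it says: "Patients with missing longitudinal data will be handled by either using data imputation methods to replace the missing data", or else that an analysis tolerant of missing values will be used. It does not choose between the two.

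Section 11.1, in a list of safety-monitoring arrangements, says: "If a subject withdraws prematurely, the data collected will not be included in the final study".

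Section 7.2 foresees withdrawal after randomisation, since "a subject may at any point elect to withdraw themselves from the study". It also lets the care team or a study physician withdraw a subject before or during the intervention period. It then deals with care: "If a subject is withdrawn from the study for any reason the subject will then be followed according to standard of care follow-up". It does not say how the data of such subjects are analysed.

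Section 8.1 plans for losses: "To account for patients dropping out or not completing the study, we will enroll 24 patients in each group", against 21 required.

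**The concern.** Intent-to-treat keeps every randomised subject in the assigned arm. Section 11.1 takes subjects out because of something that happened after randomisation, and it takes out data already in hand. An analyst who follows one rule breaks the other, and the choice could be made after the results have been seen.

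The trial describes no sham block and the outcome is a patient-reported pain score, so withdrawal could differ by arm and be related to pain. If it were, the arms compared under section 11.1 would no longer be the arms that randomisation created. The document does not show that this would happen.

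Safety recording is largely unaffected. Sections 10.1, 10.4 and 11.1 provide for recording adverse events, weekly review by the principal investigator and IRB reporting, none of which depends on a subject completing the study. One point is open: section 11.1 does not define what the withdrawn data are left out of, so it is unclear whether those subjects' adverse events appear in the final report.

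**Working it through.** **Step 1. The two rules by time of withdrawal.** Randomisation precedes the block (section 7). The primary outcome is resting NRS on POD1 (sections 1.2 and 8.1). On follow-up, section 7 says: "The patient will be contacted via phone at 24 hours, 48 hours, and 7 days".

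| Withdrawal | Section 8 | Section 11.1 | Conflict |
|---|---|---|---|
| Before randomisation | No assigned arm | Data left out | No |
| After randomisation, before the 24-hour contact | Subject stays in arm; POD1 is missing | Subject removed; baseline and any PACU scores dropped | Yes |
| After the 24-hour contact, before the day 7 call | Observed POD1 score used | Observed POD1 score deleted | Yes, on the primary outcome |
| Missed call without withdrawal | Missing-data sentence applies | Does not apply | No |

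The third row needs no missing-data method, so the conflict there does not depend on how that sentence in section 8 is read. It is unclear whether section 11.1 also covers subjects withdrawn by clinicians.

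**Step 2. The plan's sample size.** Inputs from section 8.1: difference 2 NRS, SD 2.2, alpha 0.05, power 80%. Two-sided testing is assumed because the section does not say. For a two-sample t-test with n1 and n2 subjects, the noncentrality is 2 / (2.2 × √(1/n1 + 1/n2)) on n1 + n2 − 2 degrees of freedom. Power at 20 per arm is just under 80.0% and at 21 per arm is 82.0%, so the stated 21 is reproduced. The allowance is 24 − 21 = 3 per arm, or 3/24 = 12.5%.

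**Step 3. Power if exclusions are unrelated to outcome.**

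| Analysed | Power |
|---|---|
| 24 v 24 | 86.9% |
| 24 v 23 | 86.2% |
| 23 v 23 | 85.4% |
| 24 v 21 | 84.5% |
| 21 v 21 | 82.0% |

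Power stays above 80% and the type I error stays at about 5.0%. Losses within the allowance are therefore not a power problem.

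**Step 4. Exclusions related to pain (illustration only).** Suppose k of the 24 subjects in one arm have observed POD1 scores d points above the rest of that arm, and section 11.1 removes them. The full-arm mean exceeds the mean of the rest by k × d / 24, so removal lowers the analysed mean by that amount:

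- k = 1: 1 × 2/24 = 0.08 to 1 × 3/24 = 0.13 NRS
- k = 2: 2 × 2/24 = 0.17 to 2 × 3/24 = 0.25 NRS
- k = 3: 3 × 2/24 = 0.25 to 3 × 3/24 = 0.38 NRS

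Type I error was simulated with no true difference (24 per arm, normal scores with SD 2.2 around the stated means, pooled t-test, 400,000 runs). Each cell gives d = 2, then d = 3:

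| k | Both arms contain k such subjects; only one arm's are excluded | Only one arm contains them, full-arm means equal; they are excluded | k excluded from each arm |
|---|---|---|---|
| 1 | 5.0%, 5.0% | 5.2%, 5.4% | 5.0% |
| 2 | 5.3%, 5.8% | 5.7%, 6.7% | 5.0% |
| 3 | 6.0%, 7.0% | 6.6%, 8.6% | 5.0% |

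With nobody excluded, the same data give 3.1% to 4.8%. That is below 5% because the number of high-pain subjects per arm is held fixed.

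**The case against.** The strongest reply is that the practical reach is small. An observed POD1 score is lost only if a subject actively withdraws between the 24-hour contact and the day 7 call, when little is left to withdraw from. Clinician-initiated withdrawal under section 7.2 hardly reaches that window. For earlier withdrawals no POD1 score exists, so a simple comparison of observed scores gives the same estimate under either rule. The rules then diverge on the primary estimate only if imputation or a longitudinal model is used. The missing-data sentence does not mention withdrawal and may be meant for missed contacts. The 8.6% figure needs three high-pain subjects who all withdraw from one arm after giving their scores, with none in the other arm. Nothing in the document supports that.

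Most of this stands as a limit on size. The effect on the primary estimate is firm for withdrawal after the 24-hour contact and conditional on the chosen method for earlier withdrawal. The bias is unquantified and could be nil. None of it removes the conflict with intent-to-treat, because section 11.1 is unqualified and nothing makes section 8 prevail. The allowance in section 8.1 protects power but does not say who is analysed.

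The consent pages are not available. The sentence in 11.1 may mirror wording in them, which would affect the cost of changing it.

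**Conclusion.** The contradiction holds and must be fixed. For randomised subjects who withdraw, sections 8 and 11.1 give incompatible instructions, and section 11.1 as written would delete observed primary-outcome data.

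The magnitude is unknown, since the document gives neither a withdrawal rate nor a difference between arms. The 3 per arm is a planning allowance and neither a cap nor an estimate. In the illustration, one selective exclusion has almost no effect and three in one arm move the analysed mean by 0.25 to 0.38 NRS against a target of 2. Balanced exclusions cause no bias. The rating rests on the contradiction and the loss of usable data, not on these figures. Confidence in the contradiction is high.

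**What to change.** Replace the sentence in section 11.1 with:

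> All data collected up to withdrawal from randomised subjects, whether they withdraw or are withdrawn, are retained and analysed in the assigned arm, unless the subject withdraws permission to use data already collected. All recorded adverse events are included in the final report.

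Add to section 8:

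> The primary analysis includes all randomised subjects in the assigned arm. An observed POD1 resting NRS is used whatever happens afterwards. A POD1 score missing because of earlier withdrawal is handled by the missing-data methods of this section.

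Two matters go with this. Section 8 still leaves open whether imputation or a tolerant analysis is used, so the handling of missing POD1 scores is not settled until one is named. Sections 4.2 and 7 also exclude subjects with unobtainable sonographic views, which can be discovered after randomisation. That is a separate point, but it must be reconciled with the new sentence in section 8, or a second contradiction results.

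The cost is a short text amendment with written IRB approval (section 12.6). If the consent form describes the use of data after withdrawal, its wording must be made to match, and subjects already consented on other terms would need consideration. Sample size, visits, calls and clinical care do not change.

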11.2 Data Safety Monitoring Committee

After 15 subjects have been recruited, the study data will be reviewed by an independent anesthesiologist, blinded to study arm assignment, to ensure that no safety concerns exist. In the unlikely event that there is a safety concern, study recruitment will be halted and an independent Data Safety Monitoring Committee (DSMC), consisting of a minimum of three qualified practitioners, will be convened to evaluate the safety concern and make recommendations regarding changes to the study methods or termination of the study.

Provided no safety concerns exist after 15 patients, the PI will evaluate study data every 3 months to identify patterns in the data, recruitment, withdrawals, and adverse events that might require a reassessment of study design or other action.

12. Administrative requirements

12.1 Good clinical practice

The study will be conducted in accordance with FDA and ICH guidelines for Good Clinical Practice. All study staff will be thoroughly familiar with the contents of this protocol and associated trial materials.

12.2 Data quality assurance

All study data collected by a study team member will initially be performed on a standardized case report form with a unique code. The key to the code will be stored separately. Data will be transferred to an electronic Microsoft Excel spreadsheet in coded format to a statistical analysis program. Data entry will take place on a computer in an office or screened area away from potential viewing by non-study personnel, and paper and electronic data will be kept in the primary investigator's locked office in the Department of Anesthesiology in separate locked storage. The computer will be pass-coded and linked to a secure Anesthesia Department server to allow access only to approved study personnel. All identifiable data will be destroyed as soon as it is no longer required after study publication, and de-identified data will be retained for 7 years per UW-Madison best practices.

12.3 Study monitoring

After 15 subjects have been recruited, the study data will be reviewed by an independent anesthesiologist, blinded to study arm assignment, to ensure that no safety concerns exist. In the unlikely event that there is a safety concern, study recruitment will be halted and an independent data safety board, consisting of a minimum of three qualified practitioners, will be convened to evaluate the safety concern and make recommendations regarding changes to the study methods or termination of the study.

Provided no safety concerns exist after 15 patients, the independent anesthesiologist will periodically monitor the data through the end of the study.

12.4 Ethical consideration

The study will be conducted in accordance with ethical principles founded in the Declaration of Helsinki. The IRB will review all appropriate study documentation in order to safeguard the rights, safety and well-being of the subjects. The study will only be conducted at the site where IRB approval has been obtained, specifically at UW Hospital at The American Center. The protocol, informed consent form, written information given to the patients, safety updates, annual progress reports and any revisions to these documents will be provided to the IRB by the investigator.

12.5 Patient confidentiality

Subject privacy and confidentiality will be ensured by restricting access to personal identifying study data only to members of the research team. In addition, as mentioned previously, recruitment will take place in the subject's cubicle or room in the preoperative or preprocedural holding area with the curtain drawn or door closed, in a tone of voice insufficient for others to overhear the conversation and in the presence of only those immediately accompanying the subject and those who are directly involved with the subject's care.

12.6 Investigator compliance

The investigator will conduct the trial in compliance with the protocol approved by the IRB. Changes to the protocol will require written IRB approval prior to implementation, except when the modification is needed to eliminate an immediate hazard(s) to subjects.

